### 5.2 Exclusion Criteria

Subjects are excluded from the study if any of the following criteria apply:

1. Participating in any other study and have received any other investigational drug within 30 days prior to screening or 5-half-lives, whichever is longer, or any other investigational implanted device within 30 days prior to screening, or are taking part in a nonmedication study which, in the opinion of the Investigator, would interfere with study compliance or outcome assessments.
2. Any past participation in a study that has investigated the NRG-1 pathway (e.g., Neucardin, cimaglermin).

3. Heart failure due to hypertrophic cardiomyopathy, restrictive cardiomyopathy, arrhythmogenic right ventricular dysplasia (ARVD), stress-induced ("Takotsubo") cardiomyopathy, chemotherapy-induced cardiomyopathy, peripartum cardiomyopathy, infiltrative or inflammatory cardiomyopathies, and primary valvular disease.
4. Diagnosed with medically documented acute coronary syndrome within 3 months of screening or a medically documented acute myocardial infarction within 6 months of screening.
5. Cardiac surgery, coronary artery revascularization, percutaneous coronary intervention, or valvuloplasty within 3 months prior to screening.
6. Any subject who has received an indication for coronary revascularization within 3 months prior to screening.
7. Any major surgical procedure within 1 month prior to screening or planned surgical procedure during the study period.
8. Sustained systolic BP <90 mm Hg and/or diastolic BP <50 mm Hg (confirmed by a duplicate seated reading) on at least 3 consecutive readings (office) following informed consent and prior to randomization, or overt symptomatic hypotension defined as a decrease in systolic BP of 20 mm Hg or a decrease in diastolic BP of 10 mm Hg within three minutes of standing when compared with BP from the sitting or supine position or accompanied by dizziness, syncope, blurry vision.
9. Resting HR >100 beats per minute (bpm) at Screening (Visit 1) or prior to randomization which is sustained for >15 minutes in two episodes separated by one hour of observation except in sustained atrial fibrillation when HR of up to 110 bpm is acceptable.
10. Cerebrovascular accident or hospitalizations for CV (cardiovascular) causes other than routine percutaneous procedures such as device, battery, generator changes or pacemaker lead insertion/replacement, including HF, chest pain, stroke, transient ischemic attack, or arrhythmias within 2 months prior to screening.
11. Subjects at screening have an abnormal or clinically significant 12-lead ECG abnormality, that, in the opinion of the Investigator, would affect efficacy or safety evaluation or place the subject at risk.
12. History or evidence of clinically significant arrhythmias uncontrolled by drug therapy or use of an implantable defibrillator, long QT syndrome, or evidence of QT prolongation with QTcF >450 ms for males or QTcF >470 ms for females during screening and/or prior to randomization.
13. Clinically significant renal dysfunction as measured by the estimated glomerular filtration rate of <45 mL/min/1.73m^2 as calculated by local laboratory standards (Cockcroft-Gault equation for estimation of creatinine clearance [CrCl] [Cockcroft and Gault. 1976]) at screening, or a clinically significant change in renal function between screening and baseline.
14. Clinically significant liver dysfunction as measured by: ALT >2.0 × the upper limit of normal (ULN), alkaline phosphatase > 2.0 × ULN, AST >2.0 × ULN, or GGT >2.0 × ULN or serum bilirubin ≥ 1.2 × ULN at screening, or a clinically significant change in liver function between screening and baseline.
15. Subjects with alteration of the coagulation panel (international normalized ratio [INR]) and/or prothrombin time (PT) ≥1.5 × the ULN; activated partial thromboplastin time (aPTT) ≥1.5 × ULN, or serum albumin ≤3 gm/dL. For subjects on warfarin or other anticoagulants, an INR (or PT) considered by the Principal Investigator as therapeutically appropriate will be allowed.
16. Subjects with values of total CPK and/or CK-MB >2.5x ULN per institutional standards at screening.

17. Any subject who by Investigator's judgement, has a significant hematuria or proteinuria at screening.
18. Concurrent treatment with Class Ia or III antiarrhythmic drugs (the medication must have been discontinued more than 2 months before informed consent).
19. Positive screening for human immunodeficiency virus antibodies, hepatitis B surface antigen, or hepatitis C virus antibodies.
20. Known history of or active alcohol abuse (no more than 14 units/week for males or 7 units/week for females) or use of illicit drugs within 1 year prior to randomization (excluding recreational use of marijuana or cannabidiol [CBD]-based products).
21. Other medical or psychiatric condition that, in the opinion of the Investigator, would preclude obtaining voluntary consent/assent or would confound the secondary objectives of study.
22. A history of pathologically confirmed malignancy of any type or any pathologically confirmed premalignant condition (e.g., ductal carcinoma in situ, colonic polyp with premalignant diagnosis, or cervical atypia). All subjects are to undergo cancer screening following study enrollment in accordance with American Cancer Society Guidelines (See [Section 11.0](#) Appendix 1).
23. Pregnant or lactating at screening.
24. Subjects with clinically significant or poorly controlled disease including, but not limited to, endocrine (including diabetes and thyroid) disease, neurological or psychiatric (even mild), GI, hematological, urological, immunological, or ophthalmic diseases as determined by the Investigator.
25. Subjects who are not non-smokers or light smokers (no more than 5 cigarettes per day) and who cannot abstain from smoking from 2 weeks prior to the administration of IP through the end of the study.

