### **5.3.2 Caffeine, Alcohol, and Tobacco**

Subjects with a known history of alcohol abuse will be excluded from this study. From Day 1 until completion of the 12-lead ECG and related study procedures on Day 3, subjects will abstain from ingesting caffeine- or xanthine-containing products (e.g., coffee, tea, cola drinks, and chocolate). Subject will have to abstain from ingesting caffeine- or xanthine-containing products (e.g., coffee, tea, cola drinks, and chocolate) starting 24 hours before any subsequent visit.

From Day -3 until completion of the 12-lead ECG and related study procedures on Day 3 subjects will abstain from alcohol intake and will have to abstain from alcohol intake starting 24 hours before all subsequent visits.

Subjects who use tobacco or e-cigarette products, or CBD products, will be instructed that use of nicotine-containing products (including nicotine patches) or CBD products will not be permitted from two weeks prior to IP administration until after the final follow-up visit.

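### Exclusion 1 ties the investigational-drug washout to current participation in another study, so read literally it misses subjects who recently completed or left one

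*Protocol*

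**What the plan says.** Protocol Section 5.2 applies its list disjunctively: "Subjects are excluded from the study if any of the following criteria apply". The first item is exclusion 1. Its opening part reads "Participating in any other study and have received any other investigational drug within 30 days prior to screening or 5-half-lives, whichever is longer", followed by a 30-day look-back for investigational implanted devices that hangs on the same verb. It ends with a separate limb: "or are taking part in a nonmedication study which, in the opinion of the Investigator, would interfere with study compliance or outcome assessments".

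Exclusion 2 is also about past trials, but only of one kind: "Any past participation in a study that has investigated the NRG-1 pathway".

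Three other places bear on how the wording operates:

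- Section 5.0 rules out prospective waivers of enrolment criteria, and Section 8.0 repeats that waivers are not allowed.
- Appendix 2 (Changes to the Protocol) requires the protocol to be followed exactly.
- Section 6.5 requires medication taken within 30 days before consent to be recorded, and refers questions about prior therapy to the Medical Monitor.

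**The concern.** A washout is meant for people who have stopped taking another investigational agent. By joining it to current participation with 'and', the criterion reaches only those still enrolled elsewhere and leaves out those who have just completed or left. The same structure governs the device look-back.

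This is a first-in-human safety trial with very small cohorts, so one subject carrying another experimental drug matters more than usual:

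- An event is possibly related under Table 9 if it meets one listed condition, and reasonable timing after the infusion is one of them.
- Under Section 4.6, an event at least possibly related to the investigational product can be considered a dose-limiting adverse event. The listed findings include a QTcF rise of more than 60 msec above baseline.
- An effect of the earlier drug could therefore be attributed to JK07 and enter an escalation decision.
- The SAP plans no covariate adjustment (Section V.F) and no subgroup analysis (Section V.L), so the planned analysis would not separate such a subject.

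**Working it through.** The plan states no figure on this point, so the check is one of logic, followed by an illustration.

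**1. Truth table for the drug limb.** P = participating in another study; R = other investigational drug received within the look-back.

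| P | R | Literal text (P and R) | Separate limbs (P or R) |
|---|---|---|---|
| no | no | not excluded | not excluded |
| no | yes | **not excluded** | excluded |
| yes | no | not excluded | excluded |
| yes | yes | excluded | excluded |

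The literal text excludes 1 of 4 combinations. The second row is the recent completer or leaver. The third row is a subject still enrolled elsewhere whose last dose is outside the window.

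**2. Is the second row caught elsewhere?**

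- Exclusion 2 catches it only if the earlier study was of the NRG-1 pathway.
- Appendix 4 lists recombinant neuregulins, Class 1a and Class 3 antiarrhythmics, acetaminophen and QT-prolonging drugs. It has no general entry for investigational agents.
- Section 6.5 is a recording rule and sets no washout. It also looks back only 30 days before consent. The 5-half-life arm exceeds 30 days once the half-life exceeds 30/5 = 6 days, and from there part of the intended window lies outside the recording period. SAP Section VII.I also leaves medications that ended more than 30 days before consent out of the summary table, although it lists and flags them.
- Exclusions 11 to 16 screen ECG, QTcF, renal, liver, coagulation and CPK findings. They detect some effects of a residual drug but not its presence.

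None of these is a washout.

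**3. Share of a cohort.** Active subjects per cohort are 1 sentinel + 3 randomised = 4, or 1 + 6 = 7 if expanded (Section 4.2). One affected JK07 subject is 1/4 = 25% or 1/7 = 14%.

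**4. Illustration of residual drug.** The inputs are assumptions: last dose of the other drug 10 days before screening, and a half-life of 7 to 21 days. The look-back would be 5 × 7 = 35 to 5 × 21 = 105 days, so the dose falls inside it. The fraction left is 2^(−days/half-life).

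- At screening (10 days): 2^(−10/7) = 37%; 2^(−10/21) = 72%.
- Day 1 falls 24 to 45 days after screening. The upper end is the screening limit; the lower end allows 14 days of e-Patch recording finished by Day -10. The elapsed time is therefore 34 to 55 days.
- At Day 1, half-life 7 days: 2^(−34/7) = 3.5% down to 2^(−55/7) = 0.4%.
- At Day 1, half-life 21 days: 2^(−34/21) = 33% down to 2^(−55/21) = 16%.

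For comparison, a subject exactly at the 5-half-life limit has 2^(−5) = 3.1% left at screening.

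**The case against.** The strongest reply is that exclusion 1 is a loosely drafted list: those participating, and those who have received a drug, and so on. The grammar is not parallel, and a look-back of 30 days or 5 half-lives only makes sense for past recipients. That probably was the intent, and many sites would apply it that way. But the text does not say so, and the list reading fits the rest of the sentence poorly. If participation in any other study excluded on its own, the last limb, which excludes participants in nonmedication studies only when the Investigator sees interference, would have no work to do. The literal reading has no such conflict. Sites should not have to choose between the two readings of a criterion that cannot be waived.

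It is also fair to say that the prior-medication record, the Medical Monitor contact and the screening laboratory and ECG limits reduce the harm. They do, but they do not replace the rule.

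A reader might extend the point to exclusion 25, which also uses 'and': "Subjects who are not non-smokers or light smokers (no more than 5 cigarettes per day) and who cannot abstain from smoking". The documents do not support that. A light smoker who cannot abstain does pass exclusion 25 taken alone. However, Section 5.3.2 says that nicotine-containing products "will not be permitted from two weeks prior to IP administration until after the final follow-up visit", and inclusion 11 requires the subject to be able and willing to follow the protocol. All inclusions must be met, so that subject is ineligible. A heavier smoker who can abstain is eligible, but that is a coherent rule. Section 5.3.2 expects tobacco users to enrol and stop, and sets no cigarette limit. Nothing shows that abstaining heavier smokers were meant to be barred.

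**Conclusion.** The point stands for exclusion 1 only. Read literally, its washout misses subjects who recently completed or left another investigational drug or device study, and no other section supplies one, apart from the outright bar on past NRG-1 pathway study participants. It should be corrected because it decides who may enter a first-in-human trial with 4 or 7 active subjects per cohort.

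The size is conditional. The 14% to 25% share assumes that one such subject enrols and receives JK07. The 0.4% to 33% residual at Day 1 rests on an assumed 10-day gap and assumed half-lives. These figures show what the omission could allow. They are not evidence of how often it would occur, or that any subject was affected. No sample size, analysis or other statistical figure in the plan changes.

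**What to change.** Rewrite exclusion 1 as three limbs joined by 'or':

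- currently participating in another investigational drug or device study; or
- received any other investigational drug in the 30 days or 5 half-lives before screening (whichever is longer), or any other investigational implanted device in the 30 days before screening, whether or not still participating in that study; or
- the existing nonmedication-study limb, unchanged.

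The first limb should name drug or device studies, not all interventional studies. The wider term would override the discretion that the third limb gives the Investigator over nonmedication studies. The first limb also newly excludes a subject still enrolled in another drug or device study whose last dose is outside the window; the sponsor should confirm that this is intended. The second limb alone closes the gap described here.

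The cost is one criterion reworded by amendment and possibly a few more screen failures. Exclusion 25 needs no change on this ground.

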## **5.3 Lifestyle Considerations**

### **5.3.1 Meals and Dietary Restrictions**

Subjects are required to fast for at least 10 hours prior to each visit, including the Day 1 hospital admission.

On Day 1, pre-dose assessments will be performed after a minimum 10 hour fast. A light breakfast/snack will be provided after completion of all scheduled pre-dose assessments. Subjects will receive a typical institutional lunch and dinner for a HF patient. A snack may be allowed in the evening of Day 1. The snack must be consumed to allow for a minimum 10-hour fast so that the 24-hour Day 2 procedures are clock-time matched to the extent possible to predose of Day 1 (See Table 2). Subjects should receive the same lunch, the same dinner, and the same evening snack, at as close to the same times as possible, on Day 2. Subjects must again be fasted for at least 10 hours prior to the 48-hour Day 3 study procedures.

### **5.3.2 Caffeine, Alcohol, and Tobacco**

Subjects with a known history of alcohol abuse will be excluded from this study. From Day 1 until completion of the 12-lead ECG and related study procedures on Day 3, subjects will abstain from ingesting caffeine- or xanthine-containing products (e.g., coffee, tea, cola drinks, and chocolate). Subject will have to abstain from ingesting caffeine- or xanthine-containing products (e.g., coffee, tea, cola drinks, and chocolate) starting 24 hours before any subsequent visit.

From Day -3 until completion of the 12-lead ECG and related study procedures on Day 3 subjects will abstain from alcohol intake and will have to abstain from alcohol intake starting 24 hours before all subsequent visits.

Subjects who use tobacco or e-cigarette products, or CBD products, will be instructed that use of nicotine-containing products (including nicotine patches) or CBD products will not be permitted from two weeks prior to IP administration until after the final follow-up visit.

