Randomization u	X													

Abbreviations: 2D-TTE, 2-dimensional transthoracic echocardiography;  $\beta$ -hCG, beta-human chorionic gonadotrophin; CPK-MB, creatine kinase – muscle/brain; CPK, creatine phosphokinase; ECG, electrocardiogram; HbA1c, glycosylated hemoglobin; HDL, high density lipoprotein; hs-CRP, high-sensitivity C-reactive protein; ICD, implantable cardioverter-defibrillators; IP, investigational product; LDH, lactate dehydrogenase; LDL, low density lipoprotein; PK, pharmacokinetic.

a Subjects should be admitted in the hospital study unit by 7:00 AM, or as early as practicable, on Day 1. The subject should arrive fasted (at least 10-hour fast). All baseline clinical and laboratory assessments should be conducted prior to light breakfast/snack being provided to the subject. Subjects will be scheduled for discharge on the morning of Day 3.

b Subjects will be scheduled for hospital discharge on Day 3, after completion of all planned in-patient safety, PK, and exploratory PD/biomarker assessments. However, subjects may be asked to remain in the hospital study unit for more than 48 hours after the IP administration at the Investigator's discretion.

c A full physical examination will be performed at screening. An abbreviated physical examination will be conducted at all other visits. See [Section 8.2.1](#). During screening all subjects must verify they have no prior history of malignancy and/or have undergone cancer screening or undergo cancer screening according to American Cancer Society Guidelines ([Appendix 1 Cancer Screening Guidelines](#)).

d Women of childbearing potential only.  $\beta$ -hCG blood test at screening, urine dipstick test upon admission on Day 1 prior to IP administration to confirm absence of pregnancy, and urine specimens at all time points thereafter.

e See [Section 8.2.2](#) for assessment times and parameters.

fAll AEs, including SAEs will be collected from the time of study enrollment and until 30 days after the IP administration. Following the first 30 days, only SAEs deemed at least possibly related to the study drug or study procedures should be collected. Refer to [Table 9](#) for additional details.

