**Table 2 Schedule of Digital ECG Assessments, Specimen Collection, and ECHO Assessments (Day 1 through 3)**

Schedule of Assessments (Day 1 – Day 3)			
(Order of activities to be completed left to right, top to bottom)			
Time relative to dose a	Day 1		
	12-lead ECG b	Specimen Collection (Labs)	2D-TTE
No food consumption for 10 hours before predose ECG assessment, specimen collection and ECHO			
Predose (prior to start of infusion)	X c		
		Safety (local) Biomarkers (central) PK (central) Glucose (fingerstick) Urinalysis (local) Urine β-hCG (local)	
			X
Light Breakfast/ Snack		XXXX	
Drug Infusion		XXXX	
End of infusion ( no later than 5 minutes from end-of-infusion)	X d		
		PK (central) Glucose (fingerstick)	
0.5 hour from end-of-infusion	X		
		PK (central) Glucose (fingerstick)	
1 hour from end-of-infusion	X		
		PK (central) Glucose (fingerstick)	
2 hours from end-of-infusion	X		
		PK (central) Glucose (fingerstick)	
4 hours from end-of-infusion	X		
		Safety (local) PK (central) Glucose (fingerstick)	

Schedule of Assessments (Day 1 – Day 3)			
(Order of activities to be completed left to right, top to bottom)			
	Day 1		
Time relative to dose a	12-lead ECG b	Specimen Collection (Labs)	2D-TTE
6 hours from end-of-infusion			X
8 hours from end-of-infusion	X	Safety (local) PK (central) Glucose (fingerstick)	
		Safety (local) PK (central) Glucose (fingerstick)	
12 hours from end-of-infusion		Safety (local) PK (central) Glucose (fingerstick)	
Day 2			
	12-lead ECG b	Blood Collection (Labs)	ECHO
24 hours c from end-of-infusion	X	Safety (local) Biomarkers (central) PK (central) Glucose (fingerstick) Urinalysis (local)	
		Safety (local) Biomarkers (central) PK (central) Glucose (fingerstick) Urinalysis (local)	
30 hours from end-of-infusion			X
Day 3			
	12-lead ECG b	Blood Collection (Labs)	ECHO
48 hours f from end-of-infusion	X	Safety (local) PK (central) Glucose (fingerstick)	
		Safety (local) PK (central) Glucose (fingerstick)	

Abbreviations: 2D-TTE, 2-dimensional transthoracic echocardiography; β-hCG, beta human chorionic gonadotrophin; ECHO, ECG, electrocardiogram; PK, pharmacokinetics

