### **B. Definition of Baseline**

This is a single-dose study. Unless otherwise specified, baseline is defined as the last non-missing measurement prior to study IP administration. Change from baseline will be calculated as post-baseline values minus baseline values.

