### **1. Baseline**

The baseline value will be derived as mean from triplicate ECG recordings measured prior to initiation of IP. The baseline QTc should be included in the C-QTc model as a covariate.

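### Section 5.3.2 assures fewer caffeine-free hours before the Day 1 baseline than before any assessment from Day 2 on, so uncorrected change from baseline in HR, BP and QTcF can carry a caffeine-related shift

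*Protocol*

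**What the plan says.** Protocol Section 5.3.2 has two caffeine rules. Around dosing: "From Day 1 until completion of the 12-lead ECG and related study procedures on Day 3, subjects will abstain from ingesting caffeine- or xanthine-containing products". After that, abstinence is required "starting 24 hours before any subsequent visit". No caffeine rule applies before Day 1. The same section treats its other exposures differently. For alcohol it says "From Day -3 until completion of the 12-lead ECG and related study procedures on Day 3 subjects will abstain from alcohol intake", and nicotine and CBD products stop two weeks before dosing.

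The baseline falls early on Day 1. Table 1, footnote a: "Subjects should be admitted in the hospital study unit by 7:00 AM, or as early as practicable, on Day 1". SAP Section V.B: "baseline is defined as the last non-missing measurement prior to study IP administration". For the concentration-QT analysis, SAP Section IX.B.1: "The baseline value will be derived as mean from triplicate ECG recordings measured prior to initiation of IP".

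The only other limit on intake before baseline is the 10-hour fast. Section 5.3.1 does not say whether it covers drinks. Table 2 words it as food: "No food consumption for 10 hours before predose ECG assessment, specimen collection and ECHO".

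The protocol otherwise takes care to make later readings comparable with baseline. Section 5.3.1 times the evening snack "so that the 24-hour Day 2 procedures are clock-time matched to the extent possible to predose of Day 1", and footnotes e and f of Table 2 hold the Day 2 and Day 3 ECGs to within 30 minutes of the baseline clock time, before breakfast.

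**The concern.** By requiring 24 caffeine-free hours before every later visit, the protocol itself treats caffeine as something to control when these measurements are taken. It then controls it least at the one value subtracted from all the others. A habitual user can come to baseline a few hours after the last intake and to the Day 2 and Day 3 readings after a day or two without any.

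If abstinence moves heart rate, blood pressure or QTcF, part of the recorded change from baseline would reflect that move and not the infusion. These changes belong to the primary safety endpoints. Several uses of them have no placebo correction:

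- SAP Section VII.G summarises mean ECG change from baseline by cohort with a 90% confidence interval. Vital signs are summarised by group without an interval (SAP Section VII.D).
- The QTcF change categories (30-60 and >60 ms) and the possible dose-limiting event in Protocol Section 4.6 (>60 msec above baseline) use each subject's own baseline.
- The Data Review Committee judges each sentinel, a single subject on active drug, on data that include the first 48 hours (Section 1.1). It normally reviews randomized subjects blinded (Section 9.6).

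**Working it through.** The plan gives no figure to reproduce. Two things can be checked: the caffeine-free time that the rules assure at each assessment, and where a common shift would end up.

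**1. Assured caffeine-free hours.** Inputs are the rules above plus one assumption, that the predose ECG is taken between 07:00 and 10:00. Let b be the assured hours at baseline. The clock-matched ECGs then have b + 24 ± 0.5 on Day 2 and b + 48 ± 0.5 on Day 3. Later visits have at least 24. The shortfall at baseline is 24 − b.

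| Reading of when abstinence starts | Baseline (b) | Day 2 ECG | Day 3 ECG | Later visits | 24 − b |
|---|---|---|---|---|---|
| Midnight at the start of Day 1 | 7 to 10 h | 30.5 to 34.5 h | 54.5 to 58.5 h | at least 24 h | 14 to 17 h |
| Admission at 07:00 | 0 to 3 h | 23.5 to 27.5 h | 47.5 to 51.5 h | at least 24 h | 21 to 24 h |
| 10-hour fast also bars caffeinated drinks | at least 10 h | at least 33.5 h | at least 57.5 h | at least 24 h | 14 h |

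The asymmetry survives all three readings. These are assured minimums; a subject who never takes caffeine has no difference between time points.

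**2. Where a shift would go.** Let a share u of subjects be users and let each user's reading move by s units, in either direction.

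- Within-group mean change moves by u × s. The documents give neither u nor s. Purely as an assumption, take u = 0.5 to 0.9 and s = 1 to 4 bpm or mm Hg: 0.5 × 1 = 0.5 up to 0.9 × 4 = 3.6 units. With u = 0 or s = 0 it is 0. I give no range for QTcF.
- An individual user's change moves by the full s. Against a fixed cut-off this matters only for a subject whose change would otherwise lie within s of it.
- JK07 minus placebo moves in expectation by u × s − u × s = 0, because one rule applies to everyone.
- What remains in that contrast is noise from a chance difference in the share of users, with SD = s × √[u(1 − u)(1/n₁ + 1/n₂)].

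For the noise term, an unexpanded cohort has 4 JK07 subjects (sentinel plus 3) and 1 placebo, so five such cohorts pool 5 placebo. An expanded cohort has 7 JK07 (sentinel plus 6) and 2 placebo, so seven pool 14. On the same assumptions:

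- 4 versus 5: √(1/4 + 1/5) = 0.671. Low end 1 × √(0.9 × 0.1) × 0.671 = 0.20; high end 4 × 0.5 × 0.671 = 1.34.
- 7 versus 14: √(1/7 + 1/14) = 0.463. Low end 1 × 0.3 × 0.463 = 0.14; high end 4 × 0.5 × 0.463 = 0.93.

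**3. After the change proposed below.** With b = 24 the shortfall is 24 − 24 = 0. Day 2 and Day 3 then follow about 24 + 24 = 48 and 24 + 48 = 72 hours.

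**The case against.** The strongest reply is that placebo already deals with this. The vital-sign endpoint includes a comparison with placebo, and the SAP includes placebo subjects so that background can be told apart from drug effect. SAP Section IX.B.3 plots placebo-adjusted heart rate and QTcF. The concentration-QT model in Section IX.B.4 has a treatment term and a categorical time effect, which would largely absorb a shift common to both arms. No formal hypothesis testing is planned. All of this stands. It removes the expected bias from any JK07-versus-placebo contrast, but it does not reach the uses listed above that have no such contrast.

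Second, the ECGs from the end of infusion to 8 hours fall on the same day as baseline, under the same ban. They are little affected. That stands too, and limits the point to Day 2 onward.

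Third, the fast may already keep caffeine out for 10 hours. If it covers drinks, the shortfall falls to 14 hours; it does not close.

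On the other side, a reader might infer that change from baseline has a caffeine-withdrawal shift built into it, or that the estimated drug effect is biased. The documents support neither. They give no rate of caffeine use and no effect of caffeine or abstinence on any of these measurements, and a shift shared by both arms does not bias their difference in expectation.

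**Conclusion.** The point holds as a possible, not a demonstrated, source of error. What is certain is the mismatch: about 0 to 10 assured caffeine-free hours at baseline, about 24 or more from Day 2 on, and a shortfall of 14 to 24 hours under every reading, given a predose ECG between 07:00 and 10:00. Whether it moves HR, BP or QTcF, which way and how far cannot be derived from the documents. The 0.5 to 3.6 units for a within-group mean is an illustration on assumed inputs.

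The exposure is confined to uncorrected readings from Day 2 on: within-cohort means and intervals, individual QTcF change criteria, and committee review of sentinels and blinded cohorts. Placebo contrasts are left with added noise only, an SD of about 0.2 to 1.3 units for 4 versus 5 subjects and about 0.1 to 0.9 for 7 versus 14 on the same assumptions. This is a modest point, worth acting on because the remedy is cheap and a baseline cannot be retaken after dosing.

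**What to change.** In Section 5.3.2, apply the protocol's own 24-hour caffeine and xanthine rule to the Day 1 predose assessments: start on Day -1, at least 24 hours before the predose ECG and vital signs. State whether the 10-hour fast covers drinks. Record the time of last caffeine intake at admission; neither document now asks for it.

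This gives baseline the same 24-hour minimum as later visits. It does not fully equalise Day 2 and Day 3, which would follow about 48 and 72 caffeine-free hours. The SAP should therefore say that change from baseline at those times is read against pooled placebo. For any subject already dosed, that comparison is the only remedy left.

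The cost is one more caffeine-free day per subject, a line in Section 5.3.2 and the subject instructions, one item recorded at admission, and a sentence on interpretation. No planned analysis changes.
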